10.3.1. Definition of AE

- An AE is any untoward medical occurrence in a participant administered a pharmaceutical product and which does not necessarily have a causal relationship with the study intervention. An AE can therefore be any unfavorable and unintended sign (including an abnormal laboratory finding), symptom, or disease (new or exacerbated) temporally associated with the use of a medicinal (investigational) product, or investigational combination product, whether or not related to the medicinal (investigational) product or investigational combination product.

Events meeting the AE definition

- Any abnormal laboratory test results (hematology, clinical chemistry, or urinalysis) or other safety assessments, for example, ECG, radiological scans, and vital signs measurements, including those that worsen from baseline, considered clinically significant in the medical and scientific judgment of the investigator, that is, not related to progression of underlying disease.
- Exacerbation of a chronic or intermittent preexisting condition, including either an increase in frequency and/or intensity of the condition.
- New condition detected or diagnosed after study intervention administration even though it may have been present before the start of the study.
- Signs, symptoms, or the clinical sequelae of a suspected drug-drug interaction.
- Medication error, misuse, or abuse of IMP, including signs, symptoms, or clinical sequelae.
- Lack of efficacy or failure of expected pharmacological action per se will not be reported as an AE or SAE. Such instances will be captured in the efficacy assessments. However, the signs, symptoms, and/or clinical sequelae resulting from lack of efficacy will be reported as AE or SAE if they fulfill the definition of an AE or SAE.

Events NOT meeting the AE definition

- Any clinically significant abnormal laboratory findings or other abnormal safety assessments that are associated with the underlying disease, unless judged by the investigator to be more severe than expected for the participant's condition.
- The disease or disorder being studied or expected progression, signs, or symptoms of the disease or disorder being studied, unless more severe than expected for the participant's condition.
- Situations in which an untoward medical occurrence did not occur (social and/or convenience admission to a hospital).
- Anticipated day-to-day fluctuations of preexisting disease(s) or condition(s) present or detected at the start of the study that do not worsen.

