6.4. Blinding

This is an open-label study.

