8.2.4. Clinical Safety Laboratory Tests

See Section 10.2 for the list of clinical laboratory tests to be performed and the SoA for the timing and frequency.

The investigator must review the laboratory results, document this review, and report any clinically relevant changes occurring during the study as an AE. The laboratory results must be retained with source documents unless a Source Document Agreement or comparable document cites an electronic location that accommodates the expected retention duration.

Clinically significant abnormal laboratory findings are those which are not associated with the underlying disease, unless judged by the investigator to be more severe than expected for the participant's condition.

All laboratory tests with values considered clinically significantly abnormal during participation in the study or within 7 days after the last dose of study intervention should be repeated until the values return to normal or baseline or are no longer considered clinically significant by the investigator or medical monitor.

If such values do not return to normal/baseline within a period of time judged reasonable by the investigator, the etiology should be identified and the sponsor notified.

All protocol-required laboratory assessments, as defined in Section 10.2, must be conducted in accordance with the SoA, standard collection requirements, and laboratory manual.

If laboratory values from non-protocol-specified laboratory assessments performed at an investigator-designated local laboratory require a change in participant management or are considered clinically significant by the investigator, for example, SAE or AE or dose modification, then report the information as an AE.

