8.3.3. Adverse Events of Special Interest

Adverse events of special interest for this study include

- hemorrhage
- cytopenia
- infections, and
- atrial fibrillation/atrial flutter.

More detailed information on these AEs may be found in the IB and prescribing information.

The investigator may consider modifying the dose of pirtobrutinib, for participants experiencing AESI events described in Section 6.6.

Hemorrhage***Causes of hemorrhage in this study population***

Bleeding, mainly low-grade, nonserious events of bruising and bleeding, is a recognized drug class effect of BTK inhibitor therapy.

Participant monitoring for bleeding

This study includes routine monitoring of blood count, for cases of bleeding for all participants (Section 1.3).

If a participant shows signs of bruising or bleeding, the investigator should consider checking a coagulation laboratory panel.

Cytopenia

Cytopenia is a low level of certain blood cells, such as neutropenia, anemia, or thrombocytopenia.

Causes of cytopenia in this study population

Causes of cytopenia include complications from the disease or complications from a participant's therapy. Cytopenia is a recognized drug class effect of BTK inhibitor therapy.

Individuals receiving pirtobrutinib mainly experienced neutropenia followed by anemia and thrombocytopenia.

Participant monitoring for cytopenia

This study includes routine hematologic monitoring throughout the study for all participants (Section 1.3).

If a participant develops neutropenia, the investigator should monitor the participant for increased risk of infection, as clinically appropriate.

If a participant develops thrombocytopenia, the investigator should monitor the participant for increased risk of bleeding, as clinically appropriate.

Infections

Causes of infection in this study population

Increased occurrence or severity of infections risk is a recognized risk of BTK inhibitor therapy. The risks include life-threatening, opportunistic, and fatal infections, including sepsis, and sepsis shock. These risks may increase due to a participant's underlying disease, age, prior treatment history, or comorbidities.

Participant monitoring for infections

The investigator will monitor participants throughout the study for signs of infection, particularly those with additional risk factors, such as participants that have poor bone marrow function, ongoing neutropenia, or diabetes.

Atrial fibrillation/flutter

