9.3.4. Secondary Endpoints Analysis

Duration of response

Investigator-assessed DOR is defined as the time from first documented response of CR, CRi, nPR, or PR to the first documentation of disease progression (per iwCLL 2018 criteria, Section 8.1.3) or death from any cause. Following first documentation of CR, CRi, nPR, or PR, participants who are alive and without documented disease progression at the time of the data analysis cutoff date will be censored. A detailed DOR event/censoring scheme will be provided in the SAP.

Median DOR and its CCI and DOR rates and associated CCI at selected timepoints, for each treatment group will be estimated CCI CCI

Safety analysis

Safety data will be summarized for the safety population. The baseline value for the safety analysis is defined as the value collected at the time closest to and before the start of study intervention administration.

AEs will be graded by the investigator according to the NCI CTCAE v5.0 for nonhematologic and hematologic AEs. Each AE verbatim term will be coded to a System Organ Class and a Preferred Term using the MedDRA.

All TEAEs will be summarized by treatment group, including severity and relationship to study intervention.

Summaries by treatment group will be provided for the following, but not limited to

- ≥Grade 3 AESIs
- ≥Grade 3 TEAEs
- SAEs
- discontinuations due to an AE
- dose interruptions due to an AE, and
- dose reductions due to an AE.

Estimates of key safety measures will be summarized with CCI for each treatment group.

Clinical laboratory parameters will be summarized by treatment and the worst postbaseline toxicity grade that occurs during the treatment period.

Serum immunoglobulins (IgA, IgG, and IgM) will be summarized with descriptive statistics. Participants who receive IV immunoglobulin during the study will be excluded from the summary for IgG.

Additional safety endpoints, including ECOG PS, vital signs, and weight, will be summarized descriptively with further details provided in the SAP.

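### Whether a Grade 3+ cytopenia enters the by-dose AE and AESI counts depends on an open-label investigator's judgment about CLL, and the attribution-free laboratory summary is neither tied to that endpoint nor, as worded, adjusted for baseline grade

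*Supplement*

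**What the plan says.** - **What counts as an AE.** Section 10.3.1 of the protocol counts an abnormal laboratory result as an AE when it is "considered clinically significant in the medical and scientific judgment of the investigator, that is, not related to progression of underlying disease". Its list of events that are not AEs includes "Any clinically significant abnormal laboratory findings or other abnormal safety assessments that are associated with the underlying disease", with the exception "unless judged by the investigator to be more severe than expected" for that participant.
- **Laboratory section.** Section 8.2.4 carries the same rule: "Clinically significant abnormal laboratory findings are those which are not associated with the underlying disease", with the same exception.
- **Lack of efficacy.** Section 10.3.1 adds that "clinical sequelae resulting from lack of efficacy will be reported as AE or SAE if they fulfill the definition" of an AE or SAE.
- **AESI section.** Section 8.3.3 names cytopenia as an AE of special interest and says "Causes of cytopenia include complications from the disease or complications from a" participant's therapy.
- **Where the counts are used.** In Section 3 the first secondary endpoint is Grade 3 or higher AEs, with a pointer to Section 8.3.3. Section 9.3.4 lists "≥Grade 3 AESIs" among the summaries by treatment group.
- **Who judges.** Section 6.4: "This is an open-label study". No blinded or independent adjudication of AE attribution is described.
- **What does not need attribution.** Section 9.3.4 also plans to summarize laboratory parameters by treatment and by worst postbaseline toxicity grade during treatment.

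**The concern.** In relapsed CLL a low neutrophil, platelet or hemoglobin value can be drug toxicity, uncontrolled disease, or both. Progressive marrow failure is itself one of the qualifying reasons for treatment in Section 5.1, so deciding whether a cytopenia belongs to the disease is unlikely to be a rare task. Under Sections 10.3.1 and 8.2.4 that decision determines whether the event is recorded as an AE at all.

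The trial asks whether a reduced dose improves safety without losing efficacy (Section 2.1). A dose that controls CLL less well may produce more disease-driven cytopenia, and the investigator who classifies each case knows the dose. The filter can therefore act differently in different arms. The same attribution also enters efficacy under Section 8.1.4: CRi requires the cytopenia to be related to study intervention, and platelet or hemoglobin decline counts toward PD when secondary to CLL. A cytopenia attributed to the disease can thus leave the safety table and contribute to a progression event.

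**Working it through.** **1. Do the passages conflict?** Section 8.3.3 describes causes of cytopenia and gives no recording rule. The lack-of-efficacy clause applies only when the AE definition is met, so it leads back to the same filter. Sections 10.3.1 and 8.2.4 state one rule with one exception. The wording is partly circular: 10.3.1 excludes clinically significant findings linked to the disease, while 8.2.4 reserves that term for findings not linked to it. The result is a single judgment-based rule that leaves open whether a disease-attributed Grade 3 cytopenia is an AESI.

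**2. Figures available.** Section 9.5 gives about 249 participants. The ratio, per-arm size, Grade 3+ incidence rates and power are redacted, so the plan's power statement cannot be reproduced. Assuming equal allocation, 249/3 = 83 per arm. Every rate below is an assumption.

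**3. Model.** Let D be the drug-linked Grade 3+ cytopenia rate, U the disease-linked rate (non-overlapping), and f the share of disease-linked cases recorded as AEs. The recorded rate is D + f·U. Differences are 200 mg minus the lower dose, in percentage points.

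**4. Same f in both arms.** Difference = (D200 − Dlow) − f·(Ulow − U200). When Ulow exceeds U200, the sign changes at f* = (D200 − Dlow)/(Ulow − U200), which matters only if f* < 1. With D = 20% vs 12%:

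| U at 200 mg vs lower | f = 0 | f = 0.5 | f = 1 | f* |
|---|---|---|---|---|
| 10% vs 10% | +8.0 | +8.0 | +8.0 | none |
| 8% vs 12% | +8.0 | +6.0 | +4.0 | 8/4 = 2.0 |
| 8% vs 16% | +8.0 | +4.0 | 0.0 | 8/8 = 1.0 |
| 8% vs 20% | +8.0 | +2.0 | −4.0 | 8/12 = 0.67 |

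Only the last row reverses. It needs the disease-linked excess at the lower dose (12 points) to exceed the drug-linked excess at 200 mg (8 points).

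For scale, take drug-linked cytopenia at 20% in both arms and independent disease-linked cytopenia at 5% vs 15%. Excluding disease-linked cases gives 20% vs 20%. Including them gives 1 − 0.80×0.95 = 24% vs 1 − 0.80×0.85 = 32%, a difference of −8 points. SE = √[(0.24×0.76 + 0.32×0.68)/83] = 6.9 points, so the recording rule alone moves the estimate by 8/6.9 ≈ 1.2 SE. There is no reversal here, because the starting difference is zero.

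**5. f depends on dose.** Difference = (D200 + f200·U200) − (Dlow + flow·Ulow).

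| Assumed truth | f at 200 mg / lower | Recorded rates | Difference |
|---|---|---|---|
| No difference: D = 15%, U = 10% in both | 1 / 0 | 25% vs 15% | +10 |
| same | 0 / 1 | 15% vs 25% | −10 |
| same | 0.75 / 0.25 | 22.5% vs 17.5% | +5 |
| 5-point excess at 200 mg: D = 20% vs 15%, U = 10% in both | 1 / 0 | 30% vs 15% | +15 |
| same | 0.25 / 0.75 | 22.5% vs 22.5% | 0 |
| same | 0 / 1 | 20% vs 25% | −5 |

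For 25% vs 15% (about 21 vs 12 events per 83), the chance of two-sided p < 0.05 is Φ[(0.10 − 1.96×0.0621)/0.0616] = Φ(−0.35) ≈ 36%. Here 0.0621 = √(2×0.20×0.80/83) is the pooled SE and 0.0616 = √[(0.25×0.75 + 0.15×0.85)/83] the unpooled SE.

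**6. Is the worst-grade laboratory summary enough?** With documented marrow involvement, Section 5.1 allows entry at neutrophils 0.5 ×10⁹/L, platelets 30 ×10⁹/L and hemoglobin 6 g/dL. The neutrophil and platelet limits lie inside bands that the table in Section 6.6.1 names (neutrophils <1 to 0.5 with fever or infection; platelets <50 to 25 with bleeding). Such a participant can show a high worst postbaseline grade without having worsened. Randomization balances this in expectation, so the effect is mainly dilution and noise rather than bias, but the summary then does not measure new cytopenia.

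**The case against.** The strongest reply is that the plan already holds most of the remedy. Section 9.3.4 has an attribution-free graded laboratory summary by treatment, and Section 1.3.1 schedules hematology for everyone. This stands, and it lessens the harm. A baseline shift rule is also the kind of detail Section 9 leaves to the SAP, which is not among the documents reviewed, so it cannot be called missing. What remains is that the laboratory summary is not tied to the AESI endpoint, and that Section 10.3.1 governs what sites record. A cytopenia never entered as an AE cannot be restored to the AE or AESI counts by the SAP.

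Separating progression from toxicity is also defensible, and disease-driven falls in platelets or hemoglobin are captured as PD criteria. This stands as a reason to keep attribution. It does not justify letting attribution decide whether the event is recorded.

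The weight is limited too. The primary test is ORR, and the between-dose power statement in Section 9.5 concerns all Grade 3+ treatment-emergent AEs. A participant with another such event already counts there, so a cytopenia shift would not carry over point for point.

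Two stronger readings are tempting. A reader might infer that Sections 8.3.3 and 10.3.1 flatly contradict each other. They do not, since 8.3.3 is background on causes and the lack-of-efficacy clause defers to the AE definition. A reader might also infer that the dose comparison will be reversed. No rate in the documents supports this, and in several of the settings above the sign holds and at most the size changes.

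**Conclusion.** The concern holds in limited form. Reported Grade 3+ cytopenia by dose passes through an attribution made with knowledge of the dose, and the planned laboratory summary reduces the problem without removing it.

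Size and direction are unknown because the rates are redacted. Under the assumptions shown (83 per arm, illustrative rates), dose-dependent attribution alone moves the cytopenia difference by 5 to 10 points either way. A reversal under a common recording rule needs the disease-linked excess at the lower dose to exceed the drug-linked excess at 200 mg. Under dose-dependent recording, it needs a reporting imbalance large enough to outweigh the true difference. Neither is shown to be likely.

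The point concerns a secondary safety comparison and leaves the ORR test untouched. It is confined to cytopenia; nothing examined here supports extending it to infections. It is a cheap improvement worth making.

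**What to change.** - **Section 9.3.4:** name as the main by-dose cytopenia summary the laboratory-based incidence of Grade 3+ neutropenia, anemia and thrombocytopenia (CTCAE v5.0, worsened from baseline grade), taken from the scheduled hematology regardless of attribution. Show investigator-reported cytopenia AESIs as a supplement.
- **Sections 8.3.3 and 10.3.1:** reconcile the text so that it states whether disease-attributed cytopenia is recorded as an AESI, with attribution kept as a separate field. Align Section 8.2.4 with the result, and check that it sits consistently with the attribution used for CRi and cytopenic PD in Section 8.1.4.

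The cost is a few lines of text and one derived table from data already collected. Reported cytopenia rates will be somewhat higher in all arms. The laboratory table measures cytopenia from any cause, so the attributed counts are still needed to read toxicity on its own.

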10.3.2. Definition of SAE

An SAE is defined as any untoward medical occurrence that, at any dose, meets 1 or more of the criteria listed:

- Results in death
- Is life-threatening
 - The term *life-threatening* in the definition of *serious* refers to an event in which the participant was at risk of death at the time of the event. It does not refer to an event, which hypothetically might have caused death, if it were more severe.
- Requires inpatient hospitalization or prolongation of existing hospitalization
 - In general, hospitalization signifies that the participant has been admitted to hospital or emergency ward (usually involving at least an overnight stay) for observation and/or treatment that would not have been appropriate in the physician's office or outpatient setting. Complications that occur during hospitalization are AEs. If a complication prolongs hospitalization or fulfills any other serious criteria, the event is serious. When in doubt as to whether hospitalization occurred or was necessary, the AE should be considered serious.
 - Hospitalization for elective treatment of a preexisting condition that did not worsen from baseline is not considered an AE.
- Results in persistent disability/incapacity
 - The term disability means a substantial disruption of a person's ability to conduct normal life functions.
 - This definition is not intended to include experiences of relatively minor medical significance, such as uncomplicated headache, nausea, vomiting, diarrhea, influenza, and accidental trauma, for example, sprained ankle, which may interfere with or prevent everyday life functions but do not constitute a substantial disruption.
- Is a congenital anomaly/birth defect
 - Abnormal pregnancy outcomes, for example, spontaneous abortion, fetal death, stillbirth, congenital anomalies, and ectopic pregnancy, are considered SAEs.
- Other situations
 - Medical or scientific judgment should be exercised by the investigator in deciding whether SAE reporting is appropriate in other situations such as important medical events that may not be immediately life-threatening or result in death or hospitalization but may jeopardize the participant or may require medical or surgical intervention to prevent one of the other outcomes listed in the above definition. These events should usually be considered serious.
 - Examples of such events include invasive or malignant cancers, intensive treatment in an emergency room or at home for allergic bronchospasm, blood

dyscrasias or convulsions that do not result in hospitalization, or development of drug dependency or drug abuse.

10.3.3. Definition of Product Complaints

Product complaint

A product complaint is any written, electronic, or oral communication that alleges deficiencies related to the identity, quality, durability, reliability, safety, effectiveness, or performance of a study intervention. When the ability to use the study intervention safely is impacted, the following are also product complaints:

- deficiencies in labeling information, and
- use errors for device or drug-device combination products due to ergonomic design elements of the product.

Product complaints related to study interventions used in clinical trials are collected to ensure the safety of participants, monitor quality, and to facilitate process and product improvements.

If the participant identifies a product complaint or a problem with the study intervention, investigators will instruct participants to contact the site as soon as possible so that the situation can be assessed.

An event may meet the definition of both a product complaint and an AE/SAE. In such cases, it should be reported as both a product complaint and as an AE/SAE.

Device deficiencies are product complaints.

10.3.4. Recording and Follow-Up of AE and/or SAE and Product Complaints

AE, SAE, and product complaint recording

When an AE/SAE/product complaint occurs, it is the responsibility of the investigator to review all documentation, for example, hospital progress notes, laboratory reports, and diagnostics reports, related to the event.

The investigator will then record all relevant AE/SAE/product complaint information in the participant's medical records, in accordance with the investigator's normal clinical practice. AE/SAE information is reported on the appropriate CRF page, and product complaint information is reported on the Product Complaint form.

Note: An event may meet the definition of both a product complaint and an AE/SAE. In such cases, it should be reported as both a product complaint and as an AE/SAE.

It is **not** acceptable for the investigator to send photocopies of the participant's medical records to the sponsor or designee in lieu of completion of the CRF page for AE/SAE and the Product Complaint form for product complaints.

There may be instances when copies of medical records for certain cases are requested by the sponsor or designee. In this case, all participant identifiers, with the exception of the participant number, will be redacted on the copies of the medical records before submission to the sponsor or designee.

The investigator will attempt to establish a diagnosis of the event based on signs, symptoms, and/or other clinical information. Whenever possible, the diagnosis (not the individual signs/symptoms) will be documented as the AE/SAE.

Assessment of intensity

The investigator will use CTCAE version 5.0 (NCI 2018) to assign AE severity grades.

Assessment of causality

The investigator is obligated to assess the relationship between study intervention and each occurrence of each AE/SAE. The investigator will use clinical judgment to determine the relationship.

A “reasonable possibility” of a relationship conveys that there are facts, evidence, and/or arguments to suggest a causal relationship, rather than a relationship cannot be ruled out.

Alternative causes, such as underlying disease(s), concomitant therapy, and other risk factors, as well as the temporal relationship of the event to study intervention administration will be considered and investigated.

The investigator will also consult the IB and Product Information in their assessment.

The investigator **must** review and provide an assessment of causality for each AE/SAE and document this in the medical notes.

There may be situations in which an SAE has occurred and the investigator has minimal information to include in the initial report to the sponsor or designee. However, it is very important that the investigator always make an assessment of causality for every event before the initial transmission of the SAE data to the sponsor or designee.

The investigator may change their opinion of causality in light of follow-up information and send an SAE follow-up report with the updated causality assessment.

The causality assessment is one of the criteria used when determining regulatory reporting requirements.

Follow-up of AEs and SAEs

The investigator is obligated to perform or arrange for the conduct of supplemental measurements and/or evaluations as medically indicated or as requested by the sponsor or designee to elucidate the nature and/or causality of the AE or SAE as fully as possible. This may include additional laboratory tests or investigations, histopathological examinations, or consultation with other health care professionals.

